2.1.1 General definitions

2.1.1.1 Study treatment

At Visit 2/Baseline, eligible patients will be randomized to one of the following two treatment groups in a ratio of 2:1:

Secukinumab group

Patients (or trained caregivers) will administer a dose of secukinumab 300 mg s.c. (two injections of the 150 mg PFS) once weekly for five weeks (at Baseline, Weeks 1, 2, 3, and 4), followed by dosing every four weeks, starting at Week 8 through Week 48. In order to maintain the blinding for the 12-week, placebo-controlled period, two injections of the placebo PFS will be administered at Weeks 13, 14, and 15 during the Double-blind Induction Period.

Placebo group

Patients (or trained caregivers) will administer a dose of placebo s.c. (two injections of the placebo PFS) once weekly for five weeks (at Baseline, Weeks 1, 2, 3, and 4), followed by a dose after four weeks at Week 8. Beginning at Visit 8/Week 12, all patients in the placebo group will be switched to treatment with secukinumab 300 mg s.c. Patients will receive a dose of secukinumab 300 mg s.c. (two injections of the 150 mg PFS) once weekly for five weeks (at Weeks 12, 13, 14, 15, and 16) followed by dosing every four weeks starting at Week 20 through Week 48.

Table 2-1 Overview of study treatment

Treatment group	DB Treatment Period (Rand – Wk 12 pre-dose)	DB Induction Period (Wk 12 – Wk 15)	OL Treatment Period (Wk 16 – Wk 52)
Secukinumab 300 mg			
	2x s.c. secukinumab 150 mg injection at BSL, Wks 1, 2, 3, 4 and 8	2x s.c. secukinumab 150 mg injection at Wk 12 2x s.c. PBO injection at Wks 13, 14 and 15	2x s.c. secukinumab 150 mg injection at four- week intervals from Wks 16 – 48
Placebo (PBO)			
	2x s.c. PBO injection at BSL, Wks 1, 2, 3, 4 and 8	2x s.c. secukinumab 150 mg injection at Wks 12, 13, 14, and 15	2x s.c. secukinumab 150 mg injection at four- week intervals from Wks 16 – 48

DB = Double-blind; OL = Open-label; PBO = placebo; BSL = Baseline; Wk = Week

2.1.1.2 Study day 1 and other study days

The day of first administration of the double blind randomized treatment will be considered as study day 1. All other study days will be labeled relative to study day 1. The day for a particular event on or after the study day 1 will be calculated as:

(date of event) - (date of first dose) + 1.

For example, study day 2, study day 3,..., will be one day, two days,..., after study day 1, respectively.

The day before study day 1 will be calculated as:

(date of event) - (date of first dose).

For example, study day -1, study day -2,..., will be one day, two days,..., before study day 1, respectively.

The descriptor "study day 0" will not be used.

2.1.1.3 Screening, baseline and post-baseline definitions

Screening refers to any procedures (e.g., checking inclusion and exclusion criteria) performed prior to the date of first dose of study treatment (for safety analysis) or prior to the randomization date (for efficacy analysis).

For efficacy analyses, baseline is the last assessment, i.e. the last non-missing observation, (including unscheduled visits) obtained before the randomization. All assessments obtained after randomization are considered as post-baseline unless otherwise specified.

For safety analyses, baseline is the last assessment (including unscheduled visits) obtained on or before the first dose of study treatment (i.e. treatment start date). All assessments obtained after the first dose of study treatment are considered as post-baseline unless otherwise specified.

In general, a baseline value refers to the last measurement made prior to administration of the first dose of study treatment. However, LAB assessments if no pre-treatment value exists, values obtained after first dose of treatment can be used as baseline only if it was collected on the same day as first dose.

2.1.1.4 Day of last dose of randomized study treatment

The date of last dose will be collected via the CRF. The patient's exposure will be calculated considering the end of treatment period visit (e.g., treatment completion visit). If a patient discontinued early, then the last dose + 84 days or the last visit during the study whichever occurs earlier is considered.

Duration of exposure is defined in Section 2.4.1.

2.2 Analysis sets

The following analysis sets will be used for the statistical reporting and analyses:

Randomized Set (RAN): The Randomized Set includes all randomized patients.

Safety Set (SAF): The Safety Set includes all patients who received at least one dose of study medication. Patients will be included in the analysis according to treatment received.

Full Analysis Set (FAS): The Full Analysis Set comprises all patients to whom study medication has been assigned. Patients inappropriately randomized (e.g., IRT was called in error for randomization of a screen failed patient) will be excluded from this analysis set. Following the intent-to-treat principle, patients will be analyzed according to the treatment they were assigned to at randomization.

2.2.1 Subgroup of interest

The primary efficacy variables and efficacy variables will be evaluated using randomization weight strata: "body weight <90 kg", "body weight ≥90 kg".

2.3 Patient disposition, demographics and other baseline characteristics

The summaries will be shown separately for double-blind treatment period (before or at Week 12) and open-label treatment period (after Week 12):

In double-blind treatment period 1 for following treatment groups:

Secukinumab 300 mg, Placebo, Total

In open-label treatment period 2 for following treatment groups:

Secukinumab 300 mg, Placebo / Secukinumab 300 mg and Total

No summaries for entire treatment period will be provided

2.3.1 Patient disposition

The number of patients screened will be presented along with the reasons for screen failures for all patients as specified in the screening phase disposition eCRF.

The number and percentage of patients in the randomized set (RAN) who, completed study periods (double-blind treatment period and open-label treatment period) and who discontinued the study prematurely including the reason for discontinuation will be presented for each treatment group and all patients.

Patients withdrawing consent will be listed with reason for withdrawal.

The number and percentage of patients with protocol deviations will be tabulated by treatment groups and listed separately by treatment groups.

2.3.2 Demographics

The following common demographic variables will be summarized:

Continuous variables:

- Age (years) (which is derived from year of birth and the Informed Consent date)
- Height (cm)
- Weight (kg)
- Body mass index (BMI) (kg/m**2)

Body Mass Index (BMI) will be calculated using the following formula:

• BMI = (body weight in kilograms) / (height in meters) 2

Note: For BMI, height, and body weight, the last value prior to randomization is used. If there is no weight recorded prior to taking of study treatment, BMI will be missing.

Of note: patient's height will not be remapped according to the analysis visit window.

Categorical variables:

- Body weight category ($<90 \text{ kg} / \ge 90 \text{ kg}$)
- Sex (male/female)
- Race (Caucasian/Black/Asian/Native American/Pacific Islander/Unknown/Other)

- Ethnicity (Hispanic or Latino/ Not Hispanic or Latino)
- Smoking status at baseline (Never/Current/Former)

2.3.3 Baseline disease characteristics

The following baseline disease characteristics and history of disease will be summarized for each treatment group and all patients in the Randomized Set and for Full Analysis Set.

- Baseline PASI score
- •
- Time since diagnosis of plaque psoriasis
- Psoriatic arthritis (yes, no)
- Time since diagnosis of psoriatic arthritis

The previous exposure to psoriasis treatments (biologic systemic psoriasis therapy, non-biologic systemic psoriasis therapy, topical therapy, phototherapy and photo-chemotherapy) along with body location with their duration of exposure and the reason for discontinuation will also be reported.

Unless otherwise specified, for all demographic and baseline disease characteristics, summary statistics will be presented for continuous variables for each treatment group and for all patients (total) in the Randomized Set and Full Analysis Set. The number and percentage of patients in each category will be presented for categorical variables for each treatment group and all patients (total) in the Randomized Set and Full Analysis Set.

In addition, all the above demographic and baseline disease characteristics variables will be summarized by body weight stratum (90 kg, \geq 90 kg) in the Randomized Set and Full Analysis Set.

Time since diagnosis will be calculated using the following derivation:

Duration= (Screening (Visit 1) date - date of diagnosis) + 1

Relevant medical history/current medical conditions

Any condition entered on the relevant medical history / current medical conditions CRF will be coded using the MedDRA dictionary and they will be summarized by System Organ Class (SOC) and Preferred Term (PT) in treatment group.

Summaries for cardiovascular medical history will be summarized by categories and treatment group. Frequency and the percentage of the occurrence of each category will be presented. Ongoing cardiovascular disease will be flagged.

Alcohol and Smoking history will be summarized by treatment group.

Unless otherwise specified, analyses will be based on the Safety Set.

Smoking history

Smoking history collected at Visit 1 will be summarized descriptively in terms of estimated number of pack-years based on the approximate consumption per-year.

The patient's tobacco usage status (never, current, former) will be collected and frequency and percentage of different status will be presented by treatment.

Time since last date of tobacco use (for former category) will be summarized descriptively and its duration is calculated as follows:

Date of Visit 1 - Date of last use of tobacco + 1.

Alcohol use history

Alcohol use history will be summarized descriptively in terms of estimated number of alcoholic drinks consumed per day captured at Visit 1.

Time since last date of alcohol consumption will be summarized descriptively and calculated as follows:

Date of Visit 1 – Date of last alcohol consumption + 1.

Tuberculosis risk assessment

Determination of tuberculosis (TB) status should be assessed at Visit 1. TB status must be determined by medical history, signs, symptoms and TB testing (QuantiFERON-TB Gold assay).

If the QuantiFERON-TB Gold assay test is positive or indeterminate, a TB workup will be performed.

2.4 Treatments (study treatment, rescue medication, concomitant therapies, compliance)

2.4.1 Study treatment / compliance

The analysis of study treatment and compliance data will be based on the safety set.

The number of secukinumab 1mL syringes, secukinumab placebo injections will be summarized by treatment group by means of contingency tables.

The duration in days will be summarized by treatment, descriptively and using frequencies and percentages for categories "any exposure", "≥1 week", "≥2 weeks", "≥3 weeks", "≥4 weeks", "≥8 weeks", "≥12 weeks", "≥16 weeks", "≥28 weeks", "≥40 weeks" and "≥52 weeks".

Duration of exposure will be defined as the time from first dose of study medication to the last dose plus 84 days or last visit (including follow-up visits) whichever occurs earlier, i.e., for patients who discontinued or have their last visit earlier than 84 days, the end of study

treatment exposure will be the date of the last study visit in the follow-up period or in the corresponding treatment period.

Page 14

Duration of exposure (days) = min (last study visit (including follow-up if applicable) date, last dose date +84) – first dose date +1

Duration of exposure (years) = duration of exposure (days) / 365.25

The analyses of duration of exposure described above will be done for the treatment period up to Week 12 for the interim analysis, with the last category "≥12 weeks".

Compliance of treatment:

Compliance of treatment is defined as percentage of injections administered and will be calculated as the number of injections applied (based on documented study drug administrations and syringe counts as given in the dosage administration record eCRF page) divided by the number of injections scheduled per protocol.

Compliance (%) = 100* (total no of injections administered) / (no. of injections prescribed).

Compliance to study treatment will be summarized descriptively and by categories:

<80%, and 80% - 100%, by treatment groups.

2.4.1.1 Visit windows

Visit-windows will be used for the data that is summarized by visit; they are based on the study evaluation schedule and comprise a set of days around the nominal visit day. For any assessment, there are the protocol defined scheduled visits around which visit windows were created to cover the complete range of days within the study. The visit windows are shown in Table 1-1. In this table, the days are counted since the first dose of study treatment (study days) for safety assessments, and the days are counted since the date of randomization for efficacy assessments. These visit windows apply to measurements taken at every visit. For assessments collected less often different visit windows will be applied as detailed below. When visit windows are used, all visits will be re-aligned, i.e., they will be mapped into one of the visit windows. For example, if the Week 4 visit of a patient is delayed and occurs on Day 46 instead of on Day 29, say, it will be re-aligned to visit window Week 8. In the case of major deviations from the visit schedule, or due to unscheduled visits, several assessments of a patient may fall in a particular visit window (either scheduled or unscheduled). Statistical approaches to handle multiple assessments in a given visit window are specified below.

Of note, patients are allowed to have gaps in visits.

Table 1-1	Assessment	windows	for scho	etieiv haluha
Table 1-1	Assessment	WIIIUUWS	TOT SCITE	eduled visits

Analysis Visit	Week	Scheduled Day	Visit Window	
Baseline	BSL	1	-28 to 1 day	
Week 4	4	29	Day 2-43	
Week 8	8	57	Day 44-71	
Week 12	12	85	Day 72-88	
Week 16	16	113	Day 89-141	
Week 24	24	169	Day 142-197	
Week 32	32	225	Day 198-253	
Week 40	40	281	Day 254-309	
Week 48	48	337	Day 310-351	
Week 52	52	365	Day >=352	

For data which are not collected at every visit (for ex: ______, waist circumference etc.), visit windows will be combined from above Table 1-1. For example, if an assessment is at Week 12 and Week 24 only, Week 12 visit window will extend from Day 2 to Day 88 (combining Week 1 to Week 12 visit windows); Week 24 will extend from Day 89 to Day 197 (combining Week 13 to Week 24). If more than one assessment falls into the interval, the rules defined in following section below are applied.

Assessments from treatment period 2 will not be considered for treatment period 1, and treatment period 1 visits will not be mapped into treatment period 2.

For patients who prematurely discontinued, efficacy measurements taken in follow-up period will be remapped to treatment periods.

The analysis visit will be used for listing of visit and period for safety data. If a visit falls after the last visit window (after Day376), it is not assigned an analysis visit and will be listed under label "After Week 53".

Multiple assessments within visit windows

When there are *multiple assessments* in a particular visit window, the following rules are applied to select one value "representing" the patient in summary statistics in a visit window.

• For baseline assessment:

For efficacy analyses, baseline is the last assessment (including unscheduled visits) obtained before the randomization. All assessments obtained after randomization are considered as post-baseline unless otherwise specified.

For safety analyses, baseline is the last assessment (including unscheduled visits) obtained before the first dose of study treatment. All assessments obtained after the first dose of study drug are considered as post-baseline unless otherwise specified.

- For post-baseline visit windows, the following applies (unless otherwise specified):
 - for *quantitative variables*, the *closest* to the actual visit is chosen (if two assessments have the same distance, then the earlier one will be chosen);

Page 16

- for qualitative variables, the worst record is selected. It is noted that in the analyses performed, worst case is always well defined (e.g., for urine protein values "+" and "++", the worst case is defined as "++"),
- in case qualitative variables are based on quantitative variables, e.g., , the visit will be assigned to the quantitative variable, and this visit will be used for the derived qualitative variable.

Table 2-4 Rules for selecting values for analysis

Timing of measurement	Type of data	Rule
Baseline	All data	The last measurement prior to first dose – note this may include measurements taken on the day of randomization (e.g., lab).
Post-baseline safety	Summary visit information (e.g., lab, ECG, vital etc.)	The (non-missing) measurement closest to the target day will be used.
		In the event two measurements are taken equally apart (e.g., 1 day before target date and 1 day after), the first one will be used. If two measurements are taken on the same
		day, then select the first one (using the time). If two measurements are taken on the same date/time, then use the first visit number (assuming this is the planned visit).
		If two measurements are taken on the same date/time/CRF visit, then use the average of two assessments
Post-baseline efficacy	All data	The measurement closest to the target day will be used. In the
		event two measurements are
		taken equally apart (e.g., 1 day
		before target date and 1 day
		after), the earlier one will be used.
		If two measurement are taken on the same day then select the first one using eCRF visit number.
Post-baseline safety	Summary visit information	The (non-missing) measurement closest to the

Novartis	For business use only	Page 17
SAP		0

Timing of measurement	Type of data	Rule
	(e.g., laboratory values, vital signs, etc.)	target day will be used. In the event two measurements are taken equally apart (e.g., 1 day before target date and 1 day after), the earlier one will be used.
		If two measurements are taken on the same day then select the first one (using the time).
		If two measurements are taken on the same date/time then use the first eCRF visit number (assuming this is the planned visit). If two measurements are taken on the same date/time/eCRF visit number then take the average value of these two results.
Post-baseline safety and efficacy	Notable abnormalities (e.g., vital signs, PGIC) and CTCAE grading for laboratory values	The most extreme measurement in the window will be used. Note this means a patient can have a notably high and notably low measurement within a window

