#### 3.1.2 Double-blind treatment period (Randomization to Week 12 pre-dose)

At the start of the Double-blind Treatment Period, eligible patients will be randomized via Interactive Response Technology (IRT) in a 2:1 ratio to one of two treatment arms (secukinumab 300 mg or placebo). Randomization will be stratified by body weight collected at Visit 2 (< 90 kg or  $\geq$ 90 kg).

During this period, all patients will attend study visits at Baseline, Weeks 1, 2, 3, 4, 8 and 12, and all doses of study treatment will be self-administered at the study site.

Assessments for the primary efficacy variable will be performed at Week 12 prior to patients receiving their Week 12 dose.

All patients who discontinue from the study prematurely for any reason before the end of the Double-blind Treatment Period should return to the study site for the performance of the Visit 8/Week 12 End of Treatment (EOT1) assessments. This visit should be scheduled approximately four weeks after the last dose of study treatment.

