1.1 Study design

This study uses a randomized, double-blind, placebo-controlled, parallel-group, multicenter design. The study consists of five periods:

- Screening (from 1-4 weeks before randomization);
- Double-blind Treatment Period (Randomization to Week12 pre-dose);
- Double-blind Induction Period (Week 12 post dose to Week 15 dose);
- Open-label Treatment Period (Week 16 to Week 52); and
- Follow-up Period (1 week).

A schematic of the study design is presented below:

Approximately 75 moderate to severe plaque psoriasis patients (50 in secukinumab group and 25 in placebo group) from approximately 15 sites will be randomized at Visit 2/Baseline in a 2:1 ratio

to receive secukinumab 300 mg or placebo, respectively. Randomization will be stratified by body weight collected at Visit 2 (<90 kg or ≥90 kg).

An interim analysis is planned after Week 12, which is the primary analysis time point for the study. Interim analysis will be performed after all patients have completed the Week 12 visit and the database is locked.

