2.5.3 Handling of missing values/censoring/discontinuations

For the primary efficacy variable K16 expression to the treatment at Week 12 (and other time points), a patient with a missing assessment will be considered as having a positive ("yes") response regardless of the reason for missing data (e.g., premature study discontinuation, missed visit, administrative issues). Patients who discontinue the trial for any reason will be considered as having a positive ("yes") response from the time they drop out through Week 52.

For the primary efficacy variable PASI90 response at Week 12 (and other time points), a patient with a missing assessment will be considered as a non-responder regardless to the reason for missing data (e.g., premature study discontinuation, missed visit, administrative issues). Patients who discontinuethe trial for any reason will be considered non-responders from the time they drop out through Week 52.

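### SAP Table 1-1 leaves a pre-dose Week 12 assessment on Day 89 or later without a defined analysis visit; if study day decides, observed data are imputed as failure

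*SAP*

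**What the plan says.** SAP 2.4.1.1, Table 1-1, sets Week 12 (scheduled Day 85) at Day 72-88 and Week 16 (scheduled Day 113) at Day 89-141. For variables collected less often, adjacent windows are merged. In the worked example the "Week 12 visit window will extend from Day 2 to Day 88", so the upper limit is unchanged.

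The same section has three further rules:

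- Mapping: "all visits will be re-aligned, i.e., they will be mapped into one of the visit windows", and the windows are meant "to cover the complete range of days within the study". The example is a Week 4 visit held on Day 46, which becomes Week 8.
- Period: data from period 2 are not used for period 1, and "treatment period 1 visits will not be mapped into treatment period 2".
- Unassigned visits: "If a visit falls after the last visit window (after Day376), it is not assigned an analysis visit". No other unassigned case is named.

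Period 1 is bounded by an event. SAP 1.1 describes it as "Double-blind Treatment Period (Randomization to Week12 pre-dose", and Protocol 3.1.2 says "Assessments for the primary efficacy variable will be performed at Week 12 prior to patients receiving their Week 12 dose". Protocol section 6 asks for visits as near as possible to the planned day but gives no tolerance in days.

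Under SAP 2.5.3, for PASI 90, "a patient with a missing assessment will be considered as a non-responder regardless to the reason for missing data". A missing K16 result is set to yes. SAP 2.5.2 analyses the percentage with no, so a missing K16 result also counts as a failure.

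**The concern.** A Week 12 visit held on Day 89 or later, with the assessments done before the dose, is observed randomised-phase data from before any placebo patient switches. The table excludes it from Week 12 and the period rule excludes it from Week 16. No sentence says which rule gives way.

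What is at stake is the primary estimate. If the visit is taken out of Week 12, the missing-data rule can replace an observed responder with a failure because the visit was four days late. For PASI 90 the placebo arm has almost no responders to lose, so the effect would be to shrink the difference. Two programmers could also follow the section in good faith and report different Week 12 rates from the same data.

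**Working it through.** **1. The table's own boundaries.** The inputs are the scheduled days in Table 1-1: 29, 57, 85, 113, 169, 225, 281, 337, 365. The check is whether each window ends at the midpoint (a + b)/2 of adjacent scheduled days.

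| Boundary | Midpoint | Table 1-1 |
|---|---|---|
| Week 4/8 | (29+57)/2 = 43 | 43 |
| Week 8/12 | (57+85)/2 = 71 | 71 |
| Week 12/16 | (85+113)/2 = 99 | 88 |
| Week 16/24 | (113+169)/2 = 141 | 141 |
| Week 24/32 | (169+225)/2 = 197 | 197 |
| Week 32/40 | (225+281)/2 = 253 | 253 |
| Week 40/48 | (281+337)/2 = 309 | 309 |
| Week 48/52 | (337+365)/2 = 351 | 351 |

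Seven of the eight boundaries reproduce; Week 12/16 does not. Day 88 fits the midpoint to Week 13, (85+92)/2 = 88.5, but Protocol Table 6-1 schedules no PASI, weight, vital signs or laboratory test at Week 13. The Week 12 window therefore allows 85 - 72 = 13 days early and 88 - 85 = 3 days late.

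**2. A pre-dose Week 12 visit on Day 90.** By day count it falls in Week 16. By period it belongs to period 1 and may not go to Week 16. Three readings are open:

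- (a) It has no window, so Week 12 is missing.
- (b) It goes to Week 16 by study day. This breaches the period rule and also leaves Week 12 missing.
- (c) It stays in Week 12, because every visit must be mapped and period 2 is closed to it. Nothing is imputed.

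The Day 46 example shows study day overriding the nominal visit, which favours the day count.

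**3. Whether another assessment fills Week 12.** For PASI, a Week 8 visit (Day 57) would have to be at least 72 - 57 = 15 days late, or an unscheduled PASI would have to fall in Day 72-88. For biopsies, the Protocol summary gives only Baseline, Week 12 and Week 52. The merged Week 12 window ends at Day 88 and the next biopsy window by day count is Week 52, so no other scheduled biopsy can fill the gap.

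**4. Size under (a) or (b), PASI 90.** Pooling Protocol Table 3-1:

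- Secukinumab 300 mg: (145+175+35+33)/(245+327+59+60) = 388/691 = 56.2%.
- Placebo: (3+5+0+0)/(248+326+59+61) = 8/694 = 1.2%.
- Difference: 55.0 points.

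If a share f of Week 12 visits is late in both arms and scored as failure, the loss is f x 55.0 points:

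| f (assumed) | Loss at pooled rates | Range over 54-60% vs 0-2% |
|---|---|---|
| 5% | 2.7 | 2.6-3.0 |
| 10% | 5.5 | 5.2-6.0 |
| 20% | 11.0 | 10.4-12.0 |

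With 50 secukinumab patients, each lost responder moves that arm by 1/50 = 2 points.

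**5. Scale against the planned precision.** Protocol 9.8 gives a half-width of 27.0% at a 50% event rate. With a continuity correction this reproduces: 1.96 x sqrt(0.25 x (1/50 + 1/25)) + 0.5 x (1/50 + 1/25) = 24.0% + 3.0% = 27.0%. At 56.2% and 1.2%, the normal-approximation half-width with separate variances and no correction is 1.96 x sqrt(0.562 x 0.438/50 + 0.012 x 0.988/25) = 14.4 points.

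**The case against.** A reader of Table 1-1 might infer that a late Week 12 visit has no analysis visit and is always imputed as failure. The documents do not say that. The section requires every visit to be mapped, and it names only visits after Day 376 as unassigned. Reading (c) is a fair construction, and the Day 46 example does not cross a period boundary, so it does not settle the matter. This part of the objection stands: the defect is a conflict in the text, not an explicit rule to discard.

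A reader might also infer that Day 88 is a slip for Day 99. That does not follow. Week 12/16 is the one boundary where placebo patients switch. For a placebo patient on schedule, Days 89-99 come after the first secukinumab dose on Day 85 and include the Day 92 dose. Unscheduled visits can include a PASI. A short late side may be a deliberate guard, and a plain Day 99 limit applied by day count would let post-switch data in. This stands against a simple change of number. But a guard set by day also removes pre-dose data, which need no guarding against.

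The remaining objections concern size. No visit-day distribution is given, and Protocol section 6 asks for particular care over the Week 12 visit, so the late share may be near zero. The study is exploratory and tests no hypothesis, and the illustrated shifts are smaller than the planned half-widths of 25 to 27 points. These points stand and limit the weight of the concern. They do not remove it: the primary result is an estimate with its interval, and the interval does not account for a shift caused by windowing.

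**Conclusion.** The concern holds as a conflict between rules at the primary time point. The SAP does not define what happens to a pre-dose Week 12 assessment on Day 89 or later. On the day-count reading, which the SAP's own example supports, observed pre-switch data leave Week 12 and are imputed as failure unless another assessment lies in the window. On the other reading nothing is lost.

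The loss of 2.7, 5.5 or 11.0 points rests on four assumptions: the day-count reading, late shares of 5%, 10% or 20% equal in both arms, PASI 90 rates like those in Protocol Table 3-1, and no substitute assessment in the window. The direction is towards no difference.

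It would be tempting to say the same of both primary variables. The imputation reaches K16 too, but the documents give no K16 rates, so neither the size nor the imbalance between arms can be stated for it.

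**What to change.** Before unblinding for the Week 12 analysis, amend the Week 12 row of Table 1-1 and add a rule to SAP 2.4.1.1 stating that:

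- an assessment made at the Week 12 visit before the Week 12 dose is mapped to Week 12 even if it falls after Day 88, up to a stated maximum day that is the same for all patients (for example Day 99);
- an assessment made after that dose is never mapped to Week 12;
- the same rule applies to biopsy, waist circumference and laboratory data.

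The fixed maximum is needed because a window that simply ran to the date of the dose would have no upper day limit. The bar on post-dose data is needed because the maximum day alone would admit values from after the switch.

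The cost is one table row and a short rule, with no new data. The downside is that Week 12 values would span a somewhat wider range of days: Day 72-99 instead of Day 72-88 if Day 99 is chosen.
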